4 ANALYSIS POPULATIONS

4.1 Safety Population

The Safety population is defined as subjects who received at least one dose of IMP.

4.2 PK Population

The PK population is defined as subjects who received at least one dose of INDV-2000 and have an adequate number of PK samples collected to derive at least one PK parameter. Subjects receiving placebo will not be included in the PK population.

The Food Effect PK population will be defined as the subset of Part II subjects in the PK population that have at least one evaluable PK parameter for at least one meal condition.

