### 9.6.1 Permitted Concomitant Therapies

The Investigator may prescribe concomitant medications or treatments for pain (acetaminophen up to 2000 mg per 24 hr, ibuprofen up to 600 mg per 24 hr administered orally) or nausea (promethazine 25 mg oral or suppository) as deemed necessary for the comfort of the subject. For oral therapies, please withhold dosing for at least 2 hr before or 1 hr after administration of IMP.

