## 14.3.2 Pharmacokinetic Population

The PK analysis population is defined as subjects who received at least one dose of INDV-2000 and have an adequate number of PK samples collected to derive PK parameters.

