## 14.5 Interim Analysis

No formal interim analysis is planned. In Part I, there will be a review of safety data for the sentinel group in each cohort before proceeding to the next subject in the cohort. There will also be a review of the safety and PK data for each cohort before dose escalation. The safety data review will be conducted by the DRSC (Section 15.2) using stopping rules defined in Section 6.4.

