3 STUDY DESIGN

3.1 General Description

This study will be conducted in 2 parts:

Part I: Double-blind, placebo-controlled, randomized, single ascending dose (SAD) study with INDV-2000 in fasted condition.

Healthy subjects who meet all eligibility criteria and provide informed consent will be randomized in cohorts of 8 subjects, with 6 subjects receiving active drug and 2 subjects receiving placebo. The proposed doses will be: 1 mg, 5 mg, 20 mg, 50 mg and 120 mg,

The goal for Part I is to identify the maximum well-tolerated (MTD) single dose. A sentinel group of 2 subjects will be randomized to active or placebo (1 active; 1 placebo) and will be dosed ahead of the rest of each cohort. A review of sentinel group safety data for 24 hours after dosing will be completed before IMP administration will continue in the remaining 6 subjects (5 active; 1 placebo) of each cohort.

Dose escalation decisions between cohorts will be based on a review of available safety data up to 72 hours post-dose, particularly TEAEs, vital signs, ECGs, clinical laboratory test results and PK data.

Part II: Open, cross-over, food interaction, single-dose study with INDV-2000, which will be given once under fasting conditions and once at completion of a standard FDA high-fat breakfast.

Healthy males (n=8) who meet all eligibility criteria and provide informed consent will receive IMP under fed and fasting conditions. Part II will proceed based upon an acceptable safety evaluation of Part I. The dose studied will be a well-tolerated dose studied in Part I and not exceeding the second highest tolerated dose in Part I.

A schematic depicting the study design is in Figure 1.

a=active, p=placebo, HV=healthy volunteers; SAD=Single ascending dose

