7 PHARMACOKINETIC ANALYSIS

The PK analysis will be performed for the PK population. Data listings, summaries, and figures will be done for Parts I and II separately. For Part I, data will be summarized by cohort. For Part II, data will be summarized by condition (fasted and fed).

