8.3 IMP Exposure

IMP administration will be performed on Day 1 in Part I, Part II Period 1, and Part II Period 2. Data collected will include dose, formulation, date/time, route, and whether the subject consumed remainder of 240 mL water, taste masking administered, double rinse was conducted, capsule consumption was verified, and IMP was administered per protocol. For Part II, whether the subject was fasting will also be collected.

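### As written, the PK population keeps the profile of a subject who vomits soon after oral dosing, which lowers summarised exposure and can distort the fed/fasted comparison

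*SAP*

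**What the plan says.** SAP 4.2 sets two conditions for the PK population: at least one dose of INDV-2000, and that the subject "have an adequate number of PK samples collected to derive at least one PK parameter". It names one exclusion: "Subjects receiving placebo will not be included in the PK population". Protocol 14.3.2 is built the same way, requiring that subjects "have an adequate number of PK samples collected to derive PK parameters". SAP Section 11 restates the changed definition and adds no further exclusion. The Food Effect PK population is a subset of this population, defined by evaluable parameters in at least one meal condition.

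SAP Section 7 then states: "The PK analysis will be performed for the PK population". Part I is summarised by cohort and Part II by fed or fasted condition. SAP Section 10 has the interim cohort PK follow Section 7, with nominal instead of actual times.

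Information on dose delivery is collected. SAP 8.3 records, among other items, whether "capsule consumption was verified, and IMP was administered per protocol", and SAP 8.1 collects adverse event timing. The PK population definition uses none of it. SAP 8.3 lists no vomiting field, so vomiting would be recorded only as an adverse event.

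**The concern.** INDV-2000 is given orally, as a solution or capsule. If a subject vomits before absorption is complete, the concentrations reflect an unknown fraction of the nominal dose. The subject can still give every scheduled sample, so nothing in the membership rule removes the profile.

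Cmax and AUC for that subject are then too low. CL/F is too high, because it divides the nominal dose by AUC. Dose-normalised parameters are wrong for the same reason. With six active subjects per cohort and no replacement after dosing (SAP 3.5), one such profile carries a sixth of the weight in a mean.

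Part I PK also has a stated role before escalation. Protocol 14.5 says: "There will also be a review of the safety and PK data for each cohort before dose escalation". Protocol 4.1 limits the predicted exposure of later doses. In Part II, a dose lost in only one condition would look like a food effect, or hide one.

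**Working it through.** The documents give no figure on this point and the sample size has no power basis, so there is no plan figure to reproduce. The check has two steps.

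**Step 1. Would any visible rule remove the profile?** Take an active subject who vomits early, stays in the unit and gives all 12 scheduled samples (Protocol Appendix 4).

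- SAP 4.2: dosed with INDV-2000, yes; enough samples, yes; placebo, no. The subject is in.
- SAP 7.5: AUC is dropped only if fewer than 3 consecutive concentrations are measurable. A lowered but measurable curve passes.
- SAP 7.5: parameters that need the terminal slope are dropped on fit, number of points or extrapolated area. These criteria test the shape of the terminal phase, not whether the dose was retained, so a low curve with a normal slope passes.
- SAP 9.1.2: protocol deviations are listed. No visible text links them to PK evaluability.

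The profile therefore stays in.

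**Step 2. How far do the summaries move?** Inputs: 6 active subjects per Part I cohort (SAP 3.1, "with 6 subjects receiving active drug and 2 subjects receiving placebo"); 8 subjects in Part II (SAP 3.1); fraction of normal exposure retained, f, which is an **assumption** taken as 0.50, 0.25 or 0.10. The other subjects are set to a typical exposure of 1.

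- Arithmetic mean of Cmax or AUC: (5 + f)/6
- Geometric mean: f^(1/6)

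| f | (5 + f)/6 | change | f^(1/6) | change |
|---|---|---|---|---|
| 0.50 | 0.917 | -8.3% | 0.891 | -10.9% |
| 0.25 | 0.875 | -12.5% | 0.794 | -20.6% |
| 0.10 | 0.850 | -15.0% | 0.681 | -31.9% |

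Put the other way, typical exposure is 1/0.891 = 1.12, 1/0.794 = 1.26 or 1/0.681 = 1.47 times the reported geometric mean.

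The median is more robust. In a lognormal simulation with an assumed between-subject CV of 30% it falls about 6% to 7%; at an assumed 50% it falls about 8% to 10%.

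CL/F moves up. The affected subject's value is multiplied by 1/f, provided the terminal-slope criteria are met. The geometric mean is multiplied by the same 1.12, 1.26 or 1.47. The arithmetic mean is multiplied by (5 + 1/f)/6, which is 1.17, 1.50 or 2.50.

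In Part II, with all 8 subjects contributing both periods and one dose lost in one condition, that condition's geometric mean is multiplied by f^(1/8). At f = 0.25 this is 0.841. The fed/fasted ratio falls 15.9% if the loss is in the fed period, or rises 18.9% (1/0.841 = 1.189) if it is in the fasted period.

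Excluding the affected profile returns the illustrated mean to 1.00, on five profiles in Part I.

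How often this happens is unknown. For assumed per-subject risks of 2%, 5%, 10% and 20%, the chance of at least one case among six, 1 - (1 - p)^6, is 11.4%, 26.5%, 46.9% and 73.8%.

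**The case against.** **The rule may exist where the public cannot see it.** The SAP contents list skips 7.2, the body goes from 7.6.1 to 7.7 although a food-effect section is listed, and 5.2 is cut mid-sentence. This stands as a limit. However, the population definition in 4.2 reads as complete, and its restatement in Section 11 adds nothing on dose loss.

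**The effect on escalation is inferred.** A reader might conclude that the next dose will be predicted to give less exposure than it does. The documents do not support that as a fact. No visible text says predicted exposure is computed from the cohort mean or from the PK population. SAP Section 10 says PK is outside the safety review, against Protocol 4.1, 14.5 and 15.2, SAP 3.6.1 and an earlier sentence in the same SAP section. This objection stands, so the consequence can only be stated conditionally.

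**Other safeguards exist.** Subjects are resident in Part I and an investigator is present at dosing, so early vomiting should be seen and timed. The review committee looks at adverse events, includes a PK scientist and may escalate more conservatively. Planned outputs include the median, minimum and individual profiles, so a very low curve would probably be noticed. This largely stands, with one reservation: the committee is blinded and interim PK carries subject aliases (Protocol 9.1.3, SAP Section 10), so matching a vomiting event to a low profile is not assured. Noticing a profile also does not settle whether to keep it; without a rule that choice is made after seeing the data.

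**Likelihood and size are assumed.** A reader might take the provision for "nausea (promethazine 25 mg oral or suppository" in Protocol 9.6.1 as a sign that vomiting is expected, especially at the upper doses. It is a comfort-medication provision and supports neither inference. The 31.9% figure needs the lowest assumed f and the geometric mean.

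**Conclusion.** On the visible text, the point holds for the PK summaries. Following SAP 4.2 as written puts a lost-dose profile into the cohort Cmax, AUC, dose-normalised and CL/F results, and into the Part II comparison. With one affected subject among six and an assumed 50% to 10% of exposure retained, the arithmetic mean falls 8.3% to 15.0% and the geometric mean 10.9% to 31.9%. The direction is sure only where vomiting removes drug not yet absorbed; the size depends wholly on the assumed fraction.

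For escalation the conclusion is narrower. To the extent interim PK informs predicted exposure, the error is in the non-conservative direction, and the committee's review of adverse events may catch it. The stronger claim, that escalation will be biased, is not established. The conflicting statements on whether PK enters the pre-escalation review must be reconciled before that link can be judged.

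**What to change.** In SAP 4.2, before unblinding, state that PK parameters are listed but excluded from the primary PK summaries, the food-effect comparison and the interim cohort PK when the profile has either:

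- vomiting within a stated time after dosing, for example twice the cohort median tmax; or
- a documented incomplete dose.

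Add an all-subjects summary as a sensitivity table. Do not exclude on the general per-protocol administration flag alone: SAP 8.3 also records water, rinse and taste-masking details, and a minor departure could remove a valid profile from a group of six.

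In SAP Section 10, have personnel who are already unblinded, such as those applying the subject aliases, apply the rule to the interim PK. Blinded staff then need not link an alias to an adverse event. The procedure should also say who sees the number of profiles, since a count of five beside one known vomiting event could reveal that subject's assignment. Reconcile SAP Section 10 with the protocol on whether PK enters the pre-escalation review. If a withheld section such as 7.2 already holds an exclusion rule, a cross-reference from 4.2 is enough.

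The cost is SAP wording, a vomiting time reliably recorded with the adverse event, and a short unblinded procedure for the interim step. The downside is that a cohort summary may rest on five profiles; the all-subjects table keeps the full picture.

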5 STUDY SUBJECTS

5.1 Subject Disposition

Subject disposition includes the data of informed consent version, dates of informed consent, completion status (i.e., completed or withdrawn), reason for withdrawal, reasons for screen failure.

A signed written ICF (Informed Consent Form) must be obtained from the subject or a legal representative before any study assessments or procedures may be performed. Informed consent form includes informed consent version visit, informed consent version signed, date of the informed consent signed.

If the subject has permanently discontinued study treatment and is no longer being followed for study assessments and procedures (including follow-up procedures), he/she will be considered withdrawn from the study. The primary reason for withdrawing from the study must be entered into the electronic case report form (eCRF) (e.g., subject is lost to follow-up, Indivior terminates the study or Investigator discretion). Other disposition data will include the date of the randomization, randomization number and cohort information.

Subject must meet all check-in criteria both at screening and at check-in (day -1) before entering into Part I or Part II of the study. The eCRF includes inclusion/exclusion criteria met/not, criteria and comments. A subject will be considered a screen failure if written informed consent was obtained but inclusion/exclusion criteria were not met.

5.2 **Protocol Deviations**

Protocol deviations will be collected PK sampling time deviations will be derived programmatically. Protocol deviations will be identified and documented

6 DEMOGRAPHIC AND OTHER BASELINE CHARACTERISTICS

6.1 Demographic and Other Baseline Characteristics

Demographic data will be collected during the screening of the study. Subject demographics include sex, age, ethnicity and race. Other baseline characteristics include height, weight, and BMI.

6.2 Substance Use Habits

Data will be recorded at the screening visit. Subjects will not be permitted to drink caffeinecontaining beverages, eat caffeine-containing foods or use caffeine-containing products prior to check-in through the EOS visit. In addition to 90 days prior to screening, subjects will refrain from smoking and from using e-cigarettes and nicotine-containing products through the EOS visit.

Substance use habits data collection includes category of alcohol (substance use collection date, intake status, quantity of units, and frequency), nicotine (substance use collection date, intake status, quantity of units, frequency, and substance use end date), and xanthine/caffeine (substance use collection date and intake status).

6.3 Medical History

A detailed medical history will be obtained during the screening period. Reported terms will be coded to System Organ Class (SOC) and Preferred Term (PT) using the Medical Dictionary for Regulatory Activities (MedDRA v23.0). Additional information to be collected will include start and end dates and whether the condition is ongoing.

Medical conditions, including surgeries planned before enrolment of the subject in the study, are not considered AEs if the conditions were known before study inclusion and should be reported in the subject's medical history.

Medical history collected during the screening period will include information on the subject's complete history of relevant medical conditions, diagnoses, procedures, treatments and any other noteworthy medical information. Any updates to medical history information made available during the course of the study will be captured.

6.4 **Prior Medications**

Prior medications are defined as medications taken from signing of informed consent up to time of first IMP dose. Data collected will include medication name, timing, dose, route, frequency, formulation, indication, related AEs and related medical history. Drug classes and standardized names for reported medication names will be coded using WHO-Drug Global September 2020 as defined in the study Data Management Plan (DMP).

6.5 Childbearing Potential

Data on childbearing potential will be collected for female subjects only. Data collected will include collection date, childbearing potential (yes/no), post-menopausal (yes/no), and other reason for non-childbearing potential.

6.6 Standard High Fat Breakfast

Standard high fat breakfast applies only to Part II, Period 2 of the study. Subjects should consume the entire meal in 30 minutes or less, however, the dose must be administered no later than 30 minutes after the start of the meal. Data collected will include meal type, date, time, percent of meal consumed and comment if meal not provided.

7 PHARMACOKINETIC ANALYSIS

The PK analysis will be performed for the PK population. Data listings, summaries, and figures will be done for Parts I and II separately. For Part I, data will be summarized by cohort. For Part II, data will be summarized by condition (fasted and fed).

7.1 Missing Values

The lack of a concentration value due to failure to collect the sample, a lost or compromised sample, or due to the subject's early termination from the study will be termed "missing" in the dataset, and no imputation will be done.

If the actual collection time of a postdose PK sample is inadvertently not recorded (considered as unknown), but a valid concentration value has been measured, the documentation error will be recorded as a protocol deviation, the concentration will be set to missing in the PK analysis and will be presented in listings but excluded from summary statistics.

7.3 Measurements Below the Lower Limit of Quantitation

Concentration values that are below the lower limit of quantitation (BLQ) prior to the first measurable concentration will be set to zero. The BLQ values that are between measurable concentrations will be set to missing. If two or more consecutive BLQ concentrations are followed by quantifiable concentrations, these quantified values will be set to missing. If a BLQ concentration is followed by a quantifiable concentration, and the quantifiable concentration is then followed by two or more consecutive BLQ concentrations, the quantifiable concentration will be set to missing. The BLQ values following the last quantifiable time points will be set to zero. No concentration estimates will be imputed for missing sample values.

The BLQ rules will be followed for individual and mean PK profile representations and summary statistics, but will be reported as '<LLOQ' in the concentration listings.

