#### 2.2 Secondary

The secondary objectives of this study are to:

- Determine the maximum tolerated single dose of INDV-2000
- Characterize pharmacokinetics for single doses of INDV-2000
- Determine potential effects of a high-fat meal on drug absorption and exposure

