## 5 STUDY POPULATION SELECTION

### 5.1 Number of Subjects

A sufficient number of subjects will be screened to enroll up to 80 subjects in Part I and Part II.

Part I: There will be up to 9 planned cohorts of male and non-childbearing potential female subjects. Each of the up to 9 planned cohorts will be composed of 8 subjects (6 receiving active and 2 placebo). Additional cohorts may be included but predicted exposures will not exceed the maximum exposure limits defined. Up to 72 male and female subjects will be enrolled in Part I.

Part II: Up to 8 male subjects will receive INDV-2000 on 2 occasions separated by a 1-week washout period or at least 5 half-lives whichever period is longer, once under fasting conditions and once after a standard high-fat breakfast.

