### 5.2 Inclusion Criteria

In order to participate in Part I or Part II of the study, subjects must meet the following criteria:

- 1. Must be able to verbalize understanding of the consent form, able to provide written informed consent, and verbalize willingness to complete study procedures, be able to comply with protocol requirements, rules and regulations of study site, and be likely to complete all the study interventions.
- 2. Must be considered a healthy male or non-child-bearing female for Part I.

Women of non-childbearing potential are considered women who:

- a. Do not have a uterus, or
- b. Are surgically sterile (example: has undergone complete hysterectomy, bilateral oophorectomy, or tubal ligation), or
- c. Have permanent cessation of ovarian function due to ovarian failure or surgical removal of the ovaries, or
- d. Are post-menopausal as defined by 12 months or more of spontaneous amenorrhea as confirmed by an FSH >30 mIH/mL.
- 3. For Part II, must be considered a healthy male who did not participate in Part I who is willing to consume a high-fat meal.
- 4. Between 18 and 55 years of age inclusive,
- 5. Body mass index (BMI) within 18.0 to 32.0 kg/m^2, inclusive (minimum weight of at least 50.0 kg at Screening).
- 6. Male subjects who are sexually active with female partners of child-bearing potential must use, with their partner, a condom plus an approved method of effective contraception from the time of screening until 90 days after the last dose of Investigational Medicinal Product (IMP). Additionally, male subjects must agree to not donate sperm during the study and for at least 90 days from the last dose of IMP. Effective methods of contraception are:
  - a. Combined (oestrogen and progestogen-containing) hormonal contraception associated with inhibition of ovulation:

- i. oral
- ii. intravaginal
- iii. transdermal
- b. Progestogen-only hormonal contraception:
  - i. oral
  - ii. injectable/implantable
  - iii. intrauterine hormone-releasing system (IUS)
- c. Implantable intrauterine device (IUD)
- d. Surgical sterilisation (for example, vasectomy or bilateral tubal ligation)
- e. Male condom with spermicidal gel/foam or with female cap or diaphragm (double barrier)

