## 8.10 Pharmacokinetic Assessments

## 8.10.1 Plasma Samples for Pharmacokinetic Analysis

Blood samples for PK analysis of INDV-2000 metabolite metabolite will be collected at the time points listed in Section 22.4, Appendix 4. Depending on PK results from the first dose levels, up to 2 additional samples may be added or the schedule of samples may be modified. Approximately 14 blood samples of 6 mL per sample for PK in total will be taken from any subject, however, it could be more if the subject experiences an SAE, or requires their
sample(s) retaken. The actual date and time of each sample collection will be documented. Samples will be collected into appropriate tubes as specified by the bioanalytical laboratory. Details of sample tubes, processing, storage and shipping procedures are provided in the Laboratory Manual.

Additional PK samples may be collected for subjects who experience a SAE. Samples should be collected as soon as the Investigator is made aware of the SAE and additional blood samples may be collected, after a period of time, to confirm resolution of the SAE.

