# 22.4 APPENDIX 4 – Pharmacokinetic Sampling Windows Part I

Day	Timepoint	Assessment	Window	
Day 1	pre-dose			
Day 1	0.5 hr post-dose			
Day 1	1 hr post-dose			
Day 1	2 hr post-dose			
Day 1	3 hr post-dose			
Day 1	4 hr post-dose			
Day 1	6 hr post-dose			
Day 1	8 hr post-dose			
Day 1	12 hr post-dose			
Day 2	24 hr post-dose			
Day 3	48 hr post-dose			
Day 4	72 hr post-dose			

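### SAP 7.3's consecutive-BLQ rule is not limited to samples after the first measurable concentration; read literally, BLQ at pre-dose and 0.5 h blanks the rest of an ordinary profile

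*SAP*

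**What the plan says.** SAP 7.3 handles BLQ results in five steps. BLQ values "prior to the first measurable concentration will be set to zero" (sentence 1). BLQ values lying between measurable ones become missing (sentence 2). Sentence 3 reads: "If two or more consecutive BLQ concentrations are followed by quantifiable concentrations, these quantified values will be set to missing". Sentence 4 removes a single quantifiable value that has a BLQ before it and at least two BLQs after it. Sentence 5 sets BLQ values after the last quantifiable time point to zero. The scope is then given: "The BLQ rules will be followed for individual and mean PK profile representations and summary statistics".

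Protocol Appendix 4 (22.4) schedules 12 samples per profile: pre-dose, then 0.5, 1, 2, 3, 4, 6, 8, 12, 24, 48 and 72 h. In Part I and in each Part II period, the sample right after pre-dose is "0.5 hr post-dose". Protocol 8.10.1 adds that "up to 2 additional samples may be added or the schedule of samples may be modified".

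SAP 7 summarises Part II by fasted and fed condition, and SAP 7.6.1 summarises INDV-2000 and M12 concentrations at each nominal time. One secondary objective (Protocol 2.2) is: "Determine potential effects of a high-fat meal on drug absorption and exposure".

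**The concern.** Sentences 1, 2 and 5 each say which part of the profile they cover. Sentence 3 does not. Sentence 1 does not protect the measured values, because it governs only the leading BLQ results and is silent on what follows them. A programmer can obey both at once: two zeros, then everything missing.

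The trigger is ordinary delayed absorption and needs no assay anomaly. A pre-dose sample should normally be BLQ. Part I is a single dose. A Part II subject "must be considered a healthy male who did not participate in Part I", and the Part II periods are at least 5 half-lives apart (Protocol 5.1). One BLQ at 0.5 h then completes the pair. That is plausible at the 1 mg starting dose, after a high-fat meal, or for a metabolite that must first be formed.

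If the rule is programmed as written, a slow subject's zeros stay in the mean at the early times while the later values drop out. One mean curve would then rest on different subjects before and after that point. Because only slow profiles are lost, the fed concentration summaries could misdescribe the absorption delay they are meant to show.

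**Working it through.** The plan gives no figure to reproduce, so the check applies the rule to the schedule.

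**Logic of the rule.** SAP 7.3 was coded in two versions, with sentence 4 as written in both. In the literal version, any run of two or more BLQs sets every later measured value to missing. In the limited version, only a run that starts after the first quantifiable post-dose value does so.

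For a profile that is BLQ up to its first measurable sample and measurable from then on:

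| First measurable sample | Values measured | Kept, literal | Kept, limited |
|---|---|---|---|
| 0.5 h | 11 | 11 | 11 |
| 1 h | 10 | 0 | 10 |
| 2 h | 9 | 0 | 9 |
| 4 h | 7 | 0 | 7 |

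The first measurable sample can be any of 11 post-dose times. The literal rule keeps the profile for one of them (0.5 h) and keeps nothing for the other 10.

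**All patterns.** Twelve samples give 2^12 = 4,096 BLQ/quantifiable patterns. This is a check of logic and says nothing about frequency.
- Pre-dose is BLQ in 2,048 patterns. The two versions differ in 768 of these, and 0.5 h is BLQ in all 768.
- Pre-dose and 0.5 h are both BLQ, with at least one measurable value, in 2^10 − 1 = 1,023 patterns. The literal version keeps a value in 0 of them and the limited version in 768.

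**Profiles containing the sample pair.** Protocol 5.1: "Each of the up to 9 planned cohorts will be composed of 8 subjects (6 receiving active and 2 placebo"). That gives 9 × 6 = 54 active profiles in Part I if all nine cohorts are filled. Part II gives 8 × 2 = 16. The total is 70 per analyte, or 70 × 2 = 140 for INDV-2000 and M12. These profiles contain the pair; they are not predicted to be affected.

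**Effect on a fed mean (illustration).** Suppose k of 8 fed subjects have an absorption lag and are BLQ at 0.5 h, and the other 8 − k have no lag and the same curve C(t). At the first dropped sample let r = C(t − lag)/C(t).
- Correct mean = C(t) × [(8 − k) + k·r]/8.
- Literal mean = C(t), with N = 8 − k.
- Ratio of literal to correct = 8/[(8 − k) + k·r]. It cannot exceed 8/(8 − k), which is 1.14, 1.33 and 2.00 for k = 1, 2 and 4.

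Assumptions: one-compartment curve, half-life 8 h (ke = ln 2/8 = 0.0866 per h), ka 0.5, 1 or 2 per h. Worked case: lag 0.75 h, sample at 1 h, ka 0.5. Then r = (e^(−0.0217) − e^(−0.125))/(e^(−0.0866) − e^(−0.5)) = 0.309. For k = 1 the ratio is 8/(7 + 0.309) = 1.09, and for k = 4 it is 8/(4 + 1.238) = 1.53.

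Overstatement at the first dropped sample, for ka 0.5 / 1 / 2:

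| Lag (first dropped sample) | k = 1 | k = 2 | k = 4 |
|---|---|---|---|
| 0.75 h (1 h) | 9 / 9 / 7% | 21 / 19 / 15% | 53 / 47 / 36% |
| 1.5 h (2 h) | 8 / 7 / 4% | 18 / 14 / 8% | 45 / 34 / 16% |
| 2.5 h (3 h) | 9 / 7 / 3% | 20 / 15 / 6% | 51 / 35 / 13% |

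By 6 h the lagged subjects are above the others, so dropping them makes the mean 0 to 11% too low in the same examples.

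**The case against.** The strongest reply is that the harmful reading defeats the paragraph's own purpose. Sentence 1 treats the first measurable value as the start of a usable profile. The five sentences run roughly in profile order, and sentence 3 sits between embedded and trailing BLQs. Its likely target is a late value that reappears after the drug has become unmeasurable, and applying the sentences in order would give that result. This stands as a reading of intent, but the order is not written. A programmer who follows the intent departs from the text, and one who follows the text deletes valid data.

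Sentence 3 also has a narrower literal reading, in which only the unbroken run directly after the BLQ pair is removed. Under that reading 552 of the 1,023 patterns keep at least one value, so the count of 0 depends on interpretation. An uninterrupted profile, which is the ordinary case, still loses everything.

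Three further points stand. SAP 7.3 does not name the non-compartmental analysis in its scope, so the food-effect parameters in SAP Table 1 are not shown to be affected. Listings and the reported N would expose the loss. Some Section 7 subsections are missing from the released text, so the absence of a precedence rule is established only for what can be read.

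Nothing says where any sample added under Protocol 8.10.1 would fall. One placed before 0.5 h would make the trigger easier to meet, but that is only a possibility.

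**Conclusion.** The concern holds and should be fixed. As written, BLQ at pre-dose and 0.5 h removes every measured value of an otherwise ordinary profile from the plots and concentration summaries. This part follows from the text and the sampling schedule alone.

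How many profiles would be hit is unknown, because the documents give neither the quantitation limit nor any human PK. The percentages rest on assumed ka, half-life, lag and numbers of slow subjects; only the ceilings of 14%, 33% and 100% for 1, 2 and 4 of 8 subjects hold whatever the curve. The damage is confined to descriptive output and can be found and corrected, since the measured values remain available. It still merits correction, because a pre-specified exclusion rule that selectively removes slow absorbers is wrong as stated.

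**What to change.** Open sentence 3 of SAP 7.3 with: *After the first quantifiable post-dose concentration,*. Then add: *BLQ values before the first quantifiable concentration, including pre-dose, are set to zero and do not trigger this rule.* Leave sentence 4 unchanged. Optionally, state whether 7.3 also applies to the input of the non-compartmental analysis.

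The cost is one clause, one sentence and one programming condition, with no new data. Late re-emergent values are still removed: a value at 48 h after BLQs at 12 and 24 h is dropped under both versions. Isolated values with a BLQ before and two BLQs after are still removed by sentence 4.

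There is one side effect. A profile whose only measurable value is at 48 h or 72 h would now be kept, because sentence 4 needs two later BLQ samples; the literal sentence 3 removes it. If that is unwanted, it needs its own explicit rule.
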